**Study Flow Chart (Overview):**

**Specific Drug Supply Requirements:**

For the treatment group, 140 patients will require Sugammadex for reversal of their neuromuscular blockade. The dosing for Sugammadex is 4mg/kg for a deep reversal and a 2mg/kg for a standard reversal, which will be more common for this study. Sugammadex comes in 200mg/2mL and 500mg/5mL vials. Because of the variability in weight of the patients and the type of reversal needed (deep vs standard), 140 5mL vials will be required.

**Study Duration:**

Conservatively, the Division of Gastrointestinal and Minimally Invasive Surgery group performs five laparoscopic inguinal hernia repairs per week. A total of 140 patients will receive Sugammadex in the study. If all patients undergoing laparoscopic inguinal hernia repair agreed to participate in the study, then it would require 28 weeks for all patients to have surgery. Given that not all patients will not be agreeable to participation, and to allow time for statistical analysis, we estimate that 40 weeks will be required to complete the study.

**Statistical Analysis and Sample Size Justification:**

*Variables/Time Points of Interest* – Basic demographic information for each patient will be obtained from the medical record, such as age, gender, ASA class, and prior medical histories/surgeries. This information will aid in propensity matching for the study. The propensity match will be 1:1 with an equal number of patients in each group. The match will ensure that there is no statistical difference in data points between the groups and it will be performed by our statistician using SAS. The primary outcome variable, postoperative urinary retention, is a categorical variable (yes/no) that will be documented in postoperative recovery after the patient's operation. Length of stay and hospital cost, continuous variables, will be recorded at the completion of the patient's hospital stay. Information about quality of life will be obtained postoperatively in clinic. The demographic information, primary and secondary outcomes will be entered into our institutional database along with the other information that is typically recorded, such as operative characteristics and patient follow up.

*Statistical Methods* - Data will be analyzed using Statistical Analysis Software, version 9.4 (SAS Institute, Inc., Cary, NC); this task will be performed by the statistician employed by our division. Descriptive statistics will be reported as means with corresponding standard deviations for continuous variables and percentages for categorical variables. Continuous and ordinal variables will be evaluated with the Wilcoxon-Mann Whitney and the Kruskal-Wallis tests. The Wilcoxon-Mann Whitney test will be used when normality exists and there are two variables for comparison, otherwise, the Kruskal-Wallis test will be used. For categorical variables, a Pearson chi-square will be used, and a Fisher exact test will be utilized with a small sample size (i.e. less than five). A two-sided p-value of <0.05 will be used for all significance determinations.

*Power/Sample Size* – Using SAS, the power for our study was calculated using the postoperative urinary retention rate at our institution, 7%, compared to a current 0.5% postoperative urinary retention rate using Sugammadex. With 80% power, we would need to enroll 140 patients per group. The data for this project will be interpreted by the PI for the project as well as the co-investigators.

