**Study Design/Methods:**

In this study, a prospective cohort of patients undergoing laparoscopic inguinal hernia repair will receive Sugammadex and then retrospectively be matched against a cohort of patients who did not receive Sugammadex. The patients will be matched based on age, gender, history of BPH, bilateral vs. unilateral hernia, opioid usage with morphine milliequivalents, and operative time. The patients will be consented when they present to clinic for the evaluation of their inguinal hernia as the primary means of consent or in the preoperative area as a secondary means of consent. The operating surgeon will notify the research team, consisting of a resident physician and two full time research analysts, when the patient is in clinic and expresses interest in the study. One of the members of the research team will see the patient and consent them for the study as the primary consent process. Patients will be identified prior to the day of surgery and, if not previously contacted in clinic, will be contacted via telephone about participating in the study. If the patient agrees to participate prior to the day of surgery, a member of the aforementioned research team will consent the patient on the day of surgery prior to the procedure as the secondary consent process. Inclusion and exclusion criteria are defined below. Neither the patient nor the surgeon will be blinded in this study, but we do not anticipate that this will in any way change management.

*Inclusion Criteria:*

- Over the age of 18
- Undergoing laparoscopic inguinal hernia repair at Carolinas Medical Center by attending surgeons within the Division of Gastrointestinal and Minimally Invasive Surgery
- Unilateral or bilateral inguinal hernia repair; may have concurrent umbilical hernia repair performed
- Agreeable to participation in the study

*Exclusion Criteria:*

- Patients who are having concurrent ventral or flank hernias repaired at time of operation or are having an inguinal hernia repair along with another operation (e.g. laparoscopic cholecystectomy)

- End-stage renal disease (Creatinine clearance less than 30)
- Neuromuscular disease
- Prior adverse reactions to Sugammadex
- Patients who do not provide consent for the study

[figure not shown]

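### Judging the match by the absence of a statistical difference would let an observed covariate imbalance of up to about 0.24 SD pass at 140 per group, and no adjusted analysis follows.

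*Combined protocol and SAP*

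**What the plan says.** Under Statistical Analysis and Sample Size Justification, the paragraph on variables and time points describes the match: "The propensity match will be 1:1 with an equal number of patients in each group". It then says what the match should achieve: "The match will ensure that there is no statistical difference in data points between the groups".

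The Study Design/Methods section lists the covariates: "The patients will be matched based on age, gender, history of BPH, bilateral vs. unilateral hernia, opioid usage with morphine milliequivalents, and operative time". The statistics section adds background data meant to help the matching: "age, gender, ASA class, and prior medical histories/surgeries".

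The Statistical Methods paragraph names only unpaired, unadjusted tests. For continuous and ordinal data: "Continuous and ordinal variables will be evaluated with the Wilcoxon-Mann Whitney and the Kruskal-Wallis tests". For categorical data it names Pearson chi-square, or Fisher's exact test when numbers are small. The level is set once: "A two-sided p-value of <0.05 will be used for all significance determinations".

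Neither section gives a standardised-difference limit, a caliper, a rule for re-matching, a rule for residual imbalance or a covariate-adjusted analysis of the primary outcome.

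**The concern.** A p-value answers whether a difference is larger than chance would produce at that sample size. Balance is a different question: how far apart are these particular groups on factors that drive the outcome? A difference can be non-significant and still large enough to matter. The same difference also becomes easier to pass as the groups get smaller.

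This carries more weight here than in a randomised trial. Sugammadex patients are enrolled prospectively, neostigmine patients come from chart review, and treatment is open. Matching is the only protection against confounding that the plan describes. The Background section names age, BPH, male gender and postoperative narcotic use as associated with retention, and each corresponds to a matching variable. Imbalance left in any of them passes straight into the unadjusted comparison of retention rates.

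**Working it through.** **Inputs from the protocol**
- 140 per group, 1:1, 80% power, retention 7% vs 0.5% (statistics section). Target difference: 7.0 − 0.5 = 6.5 points.
- Two-sided 0.05 with unpaired tests (Statistical Methods).
- Retention 185 of 2,551 overall, and 15.6% in the 90 patients both over 60 and with BPH symptoms (Background and Rationale).

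**Assumption.** The plan does not say which test judges balance. I use its unpaired tests at two-sided 0.05.

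**1. The plan's own figure.** Enumerated power of the two-sided Fisher exact test at 7% vs 0.5% with 140 per group is 80.3%. The 140 reproduces and is not in dispute.

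**2. Largest observed imbalance that passes, continuous covariate.** With n per group, the limit in SD units is t(0.975, 2n−2) × √(2/n).
- n=140: 1.9685 × 0.1195 = 0.235.
- n=120: 1.9700 × 0.1291 = 0.254.
- n=100: 1.9720 × 0.1414 = 0.279.

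For the planned rank test, divide by √(3/π): 0.235/0.977 = 0.241 at n=140. Both round to 0.24.

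**3. How often the test flags a real imbalance.** A true difference of 0.2 SD gives p<0.05 in 38.7% of cases at 140 per group and 29.3% at 100.

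**4. Effect on the primary outcome, at the protocol's own prevalence.**
- Events in the high-risk subgroup: 0.156 × 90 = 14. In the rest: (185 − 14)/(2,551 − 90) = 171/2,461 = 6.95%.
- Risk difference: 15.56% − 6.95% = 8.61 points.
- Prevalence: 90/2,551 = 3.5%, so about 5 of 140.
- Largest split from 5/140 with Pearson p of at least 0.05: 13/140 (p=0.051; 14/140 gives p=0.032). Standardised difference 0.23.
- Shift in retention: (8/140) × 8.61 = 0.49 points. Share of target: 0.49/6.5 = 7.6%, about 8%.

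**5. The same at an assumed higher prevalence.** The protocol gives no prevalence for BPH alone. If a factor with the same 8.61-point risk difference were present in 15.0% of one group, the largest passing split is 21/140 vs 34/140 (24.3%; p=0.0505, standardised difference 0.24). Shift: (13/140) × 8.61 = 0.80 points, and 0.80/6.5 = 12%. Both the prevalence and the transfer of the subgroup's risk difference to this factor are assumptions.

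**The case against.** **The sentence describes an intended result, not a procedure.** This is fair in part. The plan writes no accept-or-reject step and names no balance test, so the 0.24 SD depends on borrowing the outcome tests and level. It is still the only standard the plan gives for calling the match successful, and the level is stated to apply to every significance determination. A paired test would tighten the limit, but none is named.

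**Loss of pairs is hypothetical.** This stands. A reader might infer that pairs will be lost and the criterion will loosen in practice. The documents predict no such loss. The database holds 2,551 patients, about 18 per treated patient (2,551/140) before eligibility restrictions, so 140 pairs may well be obtainable. The dependence on sample size is arithmetic, and applies only if pairs are lost.

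**The bias is small.** This also stands. The standard error of the planned comparison is √[(0.07×0.93 + 0.005×0.995)/140] = 2.24 points, so 0.49 points is 0.22 standard errors and 0.80 points is 0.36. Both are upper limits for one factor. Imbalances in several factors can offset as well as add.

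**A limit of 0.10 is a convention and hard to meet.** The documents give no such figure. With 140 per group the standard error of a standardised difference is about √(2/140) = 0.12, so under pure chance about 40% of covariates would exceed 0.10. Matching can do better than chance on measured covariates, but several refits are plausible. The defect does not depend on that cut-off: any fixed limit removes the dependence on sample size.

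**Adjustment is fragile with few events.** This is correct, and it shapes the fix. Expected events are 140 × (0.07 + 0.005) = 10.5 in total, with a 0.995^140 = 50% chance of none on Sugammadex. Ordinary logistic regression could then fail through separation.

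**Conclusion.** The point holds. Under the plan's unpaired tests at two-sided 0.05, the only stated balance criterion would pass an observed difference of up to about 0.24 SD at 140 per group, and up to 0.28 SD if only 100 pairs were obtained. For the one risk factor with usable figures in the protocol, the worst passing imbalance moves retention by about 0.5 points (8% of the target difference). At an assumed prevalence of 15.0% vs 24.3% it is 0.8 points (12%).

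Two stronger conclusions are not supported. A reader might infer that the matched groups will differ by 0.24 SD. That is the most that can pass, and a good match from this database may do much better. A reader might also infer that residual imbalance could produce the planned effect by itself. The single-factor figures are far too small for that, and nothing in the documents shows several factors leaning the same way. The change is worth making because the criterion cannot show balance and no later analysis would absorb what it misses.

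**What to change.** Replace the sentence on statistical difference with text such as:

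*Balance will be assessed by absolute standardised mean differences for each pre-reversal matching covariate, against a pre-specified limit (for example 0.10, a convention). If the limit is exceeded, the propensity model or caliper will be revised before outcomes are examined. All final standardised differences will be reported. For any covariate still above the limit, a sensitivity analysis of the primary outcome will adjust for it with a method suited to sparse events (for example Firth-penalised logistic regression).*

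The cost is a short change of text and some statistician time, with no new data or patients. The match may need several refits before outcomes are viewed, and a tighter caliper may drop some pairs, with some loss of power. Control outcomes are already in the database, so the analyst should refine the match on a file without the outcome.

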### **Study Objectives**

#### *Objectives –*

1. The primary objective of this study will be to compare urinary retention rates when using Sugammadex for neuromuscular reversal compared to neostigmine. The patients receiving Sugammadex will be enrolled prospectively and those who received neostigmine will be identified retrospectively on chart review.
2. We will secondarily evaluate length of stay (in postoperative recovery or in the hospital), charges accrued by patients, and quality of life compared to patients who received neostigmine.

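### Length of stay, charges and quality of life are compared after a 1:1 propensity match with independent-sample rank tests, which are conservative to the extent that the matching covariates predict these outcomes

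*Combined protocol and SAP*

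**What the plan says.** Under Study Design/Methods, the prospective cohort "will receive Sugammadex and then retrospectively be matched against a cohort of patients who did not receive Sugammadex". The same section lists the matching variables: "The patients will be matched based on age, gender, history of BPH, bilateral vs. unilateral hernia, opioid usage with morphine milliequivalents, and operative time". The Statistical Analysis and Sample Size Justification section adds: "The propensity match will be 1:1 with an equal number of patients in each group".

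The secondary outcomes are set out under Objectives: "We will secondarily evaluate length of stay (in postoperative recovery or in the hospital), charges accrued by patients, and quality of life". The statistical section classes stay and cost as continuous: "Length of stay and hospital cost, continuous variables, will be recorded at the completion of the patient's hospital stay". The Statistical Methods paragraph then gives the only analysis for such outcomes: "Continuous and ordinal variables will be evaluated with the Wilcoxon-Mann Whitney and the Kruskal-Wallis tests". All tests are judged at two-sided 0.05. The plan names no signed-rank test, covariate-adjusted model, pair-clustered variance, effect estimate or confidence interval for these outcomes.

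**The concern.** Matching on variables that predict an outcome makes the two groups more alike on that outcome than independent samples would be. A test for independent samples ignores this, overstates the variance of the group difference, and returns p-values that are too large. Operative time, bilateral repair, age and BPH history can plausibly bear on recovery time and charges.

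The second hypothesis expects shorter stay, lower charges and no worsening of quality of life. A conservative test makes a real reduction in stay or charges easier to miss than an adjusted analysis would. For quality of life the effect runs in favour of the hypothesis: a real worsening is more likely to come out non-significant and be read as no harm.

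**Working it through.** **1. Inputs.** From the documents: 140 per group, 1:1 propensity match, six matching variables, two-sided 0.05, retention 7% vs 0.5%. Not in the documents, so assumed and varied: the within-pair correlation ρ, the share of outcome variance explained by the matching covariates (R²), a control pool of 1,500, and the shape of the outcome distribution. With two groups the Kruskal-Wallis statistic is the square of the Mann-Whitney z, so the Mann-Whitney figures below serve for both.

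**2. The plan's own figure.** Exact enumeration of Fisher's test for two independent groups at 7% vs 0.5% gives power of 79.9% at n = 139 and 80.3% at n = 140. The stated 140 is reproduced, and the planning treats the groups as independent. No power is stated for the secondary outcomes.

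**3. True alpha under direct pairing.** Under the null, pairing shrinks the variance of the rank-sum statistic by a factor of about 1 − ρs, where ρs = (6/π)·arcsin(ρ/2). So true alpha ≈ 2[1 − Φ(1.96/√(1 − ρs))]. For ρ = 0.2: ρs = 0.191, 1.96/√0.809 = 2.18, alpha ≈ 2.9%. Simulation (140 normal pairs, 20,000 runs) agrees. Power is at a shift of (1.96 + 0.842)·√[(2/140)/(3/π)] = 0.343 SD, which gives Mann-Whitney 80% at ρ = 0.

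| ρ | alpha, formula | alpha, simulated | power, Mann-Whitney | power, signed-rank |
|---|---|---|---|---|
| 0 | 5.0% | 5.0% | 79% | 79% |
| 0.1 | 3.9% | 4.0% | 80% | 83% |
| 0.2 | 2.9% | 2.8% | 82% | 88% |
| 0.3 | 2.0% | 2.1% | 84% | 92% |
| 0.5 | 0.6% | 0.6% | 88% | 98% |

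Mann-Whitney power does not fall below its own independent-sample value. The loss is relative to an analysis that uses the matching.

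**4. True alpha under a propensity match**, which is what the plan specifies (140 treated, six covariates, nearest-neighbour match on the estimated score):

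| R² | covariates unrelated to arm | covariates drive selection |
|---|---|---|
| 0.1 | 4.6% | 2.9% |
| 0.2 | 3.5% | 2.3% |
| 0.4 | 1.9% | 1.1% |

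A separate simulation with selection-driving covariates gave 4.9% at R² = 0, then 3.1%, 1.9% and 0.6% at R² = 0.1, 0.3 and 0.5. When the prognostic combination of covariates was unrelated to the score, pair correlation was near zero, yet alpha was still 4.0%, 3.4% and 2.1%. The match balances the groups even when individual pairs are not alike.

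**5. Which alternative recovers power.**
- *Signed-rank.* In that last scenario (R² = 0.1, 0.3, 0.5; shift 0.343 SD) power was 80%, 80% and 86%, against 81%, 82% and 84% for Mann-Whitney and 86%, 92% and 99% for covariate adjustment. With covariates unrelated to arm, signed-rank gained at most 1 to 3 points.
- *Missing values.* Signed-rank also drops a pair when either value is missing. At an assumed 15% missing per arm it keeps 140 × 0.85² ≈ 101 pairs, while Mann-Whitney keeps 119 per arm. At 30% it keeps 140 × 0.70² ≈ 69 against 98. With weak selection and R² = 0.2, its power was 42% and 29%, against 46% and 38%.
- *Log-scale regression.* With an assumed 8% admitted in both arms (a long upper tail) and a 0.25 SD shift in the rest, power was 17–20% against 39–40% for Mann-Whitney. If admissions instead fall from 8% to 2%, the order reverses (89–94% vs 78–82%).
- *Covariate-adjusted, pair-clustered analysis on ranks.* Alpha was 3.4–6.4%. Power was 55–75% vs 51–57% for Mann-Whitney with normal outcomes, and 41–53% vs 39–40% with the admission tail. It matched or beat Mann-Whitney in every scenario run.

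**6. Primary outcome.** Here too the planned test is unpaired: "For categorical variables, a Pearson chi-square will be used, and a Fisher exact test will be utilized with a small sample size". At 7% vs 0.5% and n = 140, Fisher vs exact McNemar power is 80.3% vs 80.7% at pair correlation 0, and 81.2% vs 84.0% at 0.1. The difference is under 3 points.

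**The case against.** The strongest reply has four parts.

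First, everything depends on how well the covariates predict the outcomes, and the documents do not say. That stands. A reader might infer that the true alpha is certainly below 5% and that power is certainly lost. The documents support neither: with no association there is no effect, and Mann-Whitney keeps at least its independent-sample power.

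Second, the controls are historical. A reader might infer that the overall false-positive risk is below 5%. The calculations cover sampling error only. Residual confounding or change over calendar time could push the error in either direction, and is a separate issue.

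Third, the obvious replacements are not free gains. This stands for signed-rank alone and for log-scale regression as the only test. It does not stand against adjustment on the rank scale.

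Fourth, these are secondary outcomes, the error is conservative, and it cannot by itself create a false claim of benefit. That is right and limits the weight of the point. It does not remove the quality-of-life problem, where a missed difference supports the hypothesis. That problem comes mainly from reading non-significance as no harm, so an interval is needed whichever test is used.

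**Conclusion.** The point holds in conditional form. The planned tests ignore a match that the design builds deliberately, and they are conservative when the matching covariates are prognostic. Under the assumed propensity-match settings, a nominal 5% test runs at about 3–4.6% if R² is 10% and at 1–2% if R² is 40%, with no loss at zero. The direction, for sampling error alone, is secure whenever the covariates matter. The size is a range because the documents give no R² or pair correlation.

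A reader might extend this to urinary retention because that test is also unpaired. The check does not support a finding there: power moves by less than 3 points at pair correlations of 0 to 0.1. The secondary outcomes have no stated power, so no figure in the plan is overturned.

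**What to change.** In the Statistical Methods paragraph, make the main comparison for length of stay, charges and quality of life a covariate-adjusted analysis that keeps the rank basis, such as rank ANCOVA or a proportional-odds model. Include reversal agent, age, gender, BPH history, laterality and operative time, with standard errors clustered on the matched pair. Opioid use is left out of the model because the plan does not say when it is measured, and it may include use after reversal.

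Report an adjusted effect estimate with its 95% confidence interval for each outcome. State that the quality-of-life hypothesis will be judged from the interval and not from a non-significant p-value. Keep the unadjusted Mann-Whitney test as a sensitivity analysis. Do not rely on signed-rank alone, and do not make log-scale regression the only test.

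The cost is SAP wording and a few lines of SAS. No extra patients or data are needed, because the covariates are already collected for the match. The pair identifier must be kept in the analysis file and the model form fixed in advance. If the covariates turn out not to be prognostic, the gain is near zero.

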Sugammadex has been anecdotally reported to decrease rates of postoperative urinary retention following laparoscopic inguinal hernia repair. The more rapid reversal of neuromuscular blockade helps to explain this claim. In other areas of surgery, such as orthopedics, Sugammadex has already been associated with reduced anticholinergic usage and decreased rates of postoperative urinary retention. The cost efficacy of Sugammadex has yet to be determined as it is more expensive than traditional reversal counterparts; however, if it significantly decreases rates of postoperative urinary retention it could reduce healthcare costs that are downstream. Given that the reported incidence of postoperative urinary retention is high after laparoscopic inguinal hernia repair, and given this is one of the most common general surgery operations performed, the results of this study will certainly be widely applicable.

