#### *Hypotheses –*

1. We hypothesize that the use of Sugammadex as a neuromuscular reversal agent will decrease postoperative urinary retention after laparoscopic inguinal hernia repair compared to patients who received neostigmine.
2. We also hypothesize that there will be decreased postoperative length of stay, total hospital charges accrued by patients, and no negative impact on quality of life compared to patients who received neostigmine.

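### Only rank tests are named for hospital charges, although the plan reports means and hypothesises lower total charges; the misstated choice between the two rank tests changes no p-value by itself

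*Combined protocol and SAP*

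**What the plan says.** Statistical Methods, within Statistical Analysis and Sample Size Justification, names two tests for outcomes of this type: "Continuous and ordinal variables will be evaluated with the Wilcoxon-Mann Whitney and the Kruskal-Wallis tests". It chooses between them as follows: "The Wilcoxon-Mann Whitney test will be used when normality exists and there are two variables for comparison, otherwise, the Kruskal-Wallis test will be used". The same paragraph sets the summary statistics: "Descriptive statistics will be reported as means with corresponding standard deviations for continuous variables and percentages for categorical variables". Under Variables/Time Points of Interest: "Length of stay and hospital cost, continuous variables, will be recorded at the completion of the patient's hospital stay".

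The Hypotheses section expects that with sugammadex "there will be decreased postoperative length of stay, total hospital charges accrued by patients". Background and Rationale says of sugammadex that "it is more expensive than traditional reversal counterparts" and looks for an offsetting saving downstream if retention falls.

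No section adds a t-test, regression model, bootstrap, transformation or median for charges. Funding Source says that the study budget covers the drug. Study Design/Methods takes patient cost from a monthly billing statement. Neither says whether the drug appears on the patient's bill.

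**The concern.** Two things are wrong, and they differ in weight.

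The rule is misstated. Wilcoxon-Mann-Whitney is a rank test and does not require normality. Kruskal-Wallis extends it to three or more groups and is not what one turns to when normality fails. The two variables in the rule are presumably two groups, and this study has only two.

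The heavier point is what the rule leaves out. A normality condition normally separates a test of means from a rank test; here both branches are rank tests. Total charges are a matter of means, because the cost argument is that a dearer drug may pay for itself by preventing a few expensive events. A rank test gives those events little weight, since a patient whose charge doubles counts little more than one whose charge is slightly above the rest. At stake is whether the test answers the cost hypothesis and agrees with the means printed beside it.

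**Working it through.** **The plan's own figure.** The only sample-size figure is 140 per group for retention, 7% against 0.5%, 80% power, two-sided 0.05. Exact power of Fisher's test is 79.9% at 139 and 80.3% at 140 per group, so 140 reproduces. The plan gives no standard deviation or power for charges.

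**Step 1: does the mix-up matter by itself?** For two groups the Kruskal-Wallis statistic is the square of the Wilcoxon-Mann-Whitney z (asymptotic, no continuity correction). On 500 simulated data sets with ties, 140 per group, the two p-values differed by less than 1e-12. Either branch gives the same answer.

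**Step 2: when do mean and rank part?** Let d be the extra drug charge in every sugammadex patient and R the extra charge of a retention event.

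- Change in mean charge = d − (0.07 − 0.005) × R = d − 0.065R. The mean falls once R > d / 0.065 = 15.4d.
- With no other variation and 0 < d < R, a random sugammadex patient costs more than a random control with probability 0.93 + 0.07 × 0.005 = 0.930, and less with probability 0.07 × 0.995 = 0.070.

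So the mean can favour sugammadex while the ranks point the other way. Spread in base charges weakens this, so its size has to be simulated.

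**Step 3: simulation on assumed charges.** From the plan: retention 7% and 0.5%, 140 per group, two-sided 0.05. Assumed, because the documents give no charges: lognormal base charge with mean 1, R = 1 (retention doubles the charge), d = 0, 0.02 or 0.05, and the base coefficient of variation (CV) shown. Groups are drawn independently, and Welch's test stands in for a test of means. True changes in mean charge are −0.065, 0.02 − 0.065 = −0.045, and 0.05 − 0.065 = −0.015.

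Drug not billed (d = 0), share of trials finding the saving:

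| Base CV | Rank test | Test of means |
|---|---|---|
| 10% | about 15% | about 75% |
| 15% | about 15% | about 65% |
| 20% | about 15% | about 52% |
| 30% | about 15% | about 33% |
| 50% | about 15%, or slightly less | about 18% |

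Drug billed, share of trials in which the rank test is significant for dearer **and** the observed mean is lower:

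| Base CV | d = 5% of base | d = 2% of base |
|---|---|---|
| 10% | about 53% | about 6% |
| 15% | about 11% | about 1% |
| 20% | about 1% | about 0.2% |
| 30% | about 0% | about 0% |

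With d = 2%, the saving is found in about 25% of trials by Welch and 3.6% by the rank test at CV 20%, and in about 18% and 5% at CV 30%.

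**The case against.** The best defence has four parts.

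*The stated error is harmless.* This stands for the choice between the two tests. A reader might infer that the swapped rule produces wrong p-values; it does not. Rank tests are also acceptable for length of stay and quality-of-life scores.

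*The drug may not be in the charges.* This stands too. The study budget pays for it and billing is not stated. With d = 0 the rank test is significant for dearer in only 0.1 to 0.3% of trials, so the reversal disappears. The loss of power does not.

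*A reversal needs tightly clustered charges.* This stands. With d = 5% the rank test is significant for dearer in about 80%, 37% and 17% of trials at CV 10%, 15% and 20%. A reader might take these as the rate at which test and reported mean contradict each other. They are not, because they include trials in which the observed mean was also higher. The contradiction itself occurs in about 53%, 11% and 1%, and in none from CV 30%. Study Design/Methods admits unilateral, bilateral and concurrent umbilical repairs, which is a reason to consider the wider spreads.

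*A test of means may find little.* This stands in part. With d = 5% the net saving is 1.5% of the base charge, and a test of means detects it in only about 4 to 7% of trials. It would still estimate the quantity hypothesised.

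**Conclusion.** The concern holds as a mismatch between hypothesis, summary and test for hospital charges. The normality condition and Kruskal-Wallis are errors of wording with no numerical effect in a two-group comparison. The lack of any comparison of means does have an effect: if the drug is not billed and retention doubles the charge, the planned test finds a real saving in about 15% of trials, where a test of means finds it in about 75% down to 18% as base CV rises from 10% to 50%.

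The documents do not support saying that the cost test will point opposite to the reported means. That needs the drug to be billed, a surcharge that is sizeable relative to the spread, and a low CV; none of these is given. It is a possibility, common only at CV of about 10% to 15% with a 5% surcharge.

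All sizes rest on assumed charges and independent groups. Charges are a secondary outcome, so the retention comparison and the 140 per group are unaffected. The change is worth making before analysis, because cost is a named objective and hypothesis.

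**What to change.** In Statistical Methods, delete the normality condition and the Kruskal-Wallis test. For hospital charges, make the primary comparison the difference in arithmetic means with a bootstrap 95% confidence interval that resamples matched pairs. State whether the cost of the drug is included in the charges analysed. Keep a Wilcoxon test for length of stay and quality of life, and report medians with interquartile ranges beside it.

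This costs a few sentences and routine SAS code, with no change to enrolment. The statistical price is a wide interval for mean charges, because retention events are few. If the surcharge is near 5%, the study is unlikely to show a net saving by any method, and the plan should say so.
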